Patients randomly assigned into the treatment group will undergo open or arthroscopic rotator cuff repair with A-FLEX graft to augment the repair. ECM scaffold grafts are indicated for the reinforcement of soft tissues repaired by sutures or suture anchors during tendon repair surgery, including rotator cuff.

3. Alternative Treatment Group

Patients who meet pre-op inclusion criteria where a repair cannot be accomplished due to intraoperative findings will remain in the study. This group will be analyzed separately and still follow study procedures.

E. Surgical Methods

Prior to repair

Tendon qualities and measurements will quantified and recorded:

- Tear size, retraction, quality of tissue

Arthroscopic Primary Rotator Cuff Repair

All patients will undergo arthroscopic primary repair using a suture bridge technique. An acromioplasty, distal clavicle excision and biceps tenodesis or tenotomy may be performed by routine techniques as clinically indicated. The tendon tear will be identified and mobilized, as indicated, such that the tendon can be approximated over the greater tuberosity. Standard double row suture bridge fixation technique will be used for all repairs

Mini-open/ Arthroscopic Graft Augmentation

In patients receiving a graft, thru mini open technique the lateral portal incision will be extended vertically approximately 5-6 cm. A standard, deltoid-splitting, mini-open approach will then be performed, leaving the deltoid attachment to the acromion intact. For arthroscopic technique same method of fixation will be used below. The dermis graft will be sized and cut so as to cover the entire repair site in both medial-lateral and anterior-posterior dimensions. The medial sutures previously placed in the tendon at the time of arthroscopic repair will then be passed in a mattress technique through the medial side of the graft. At least two

mattress sutures will be used, bringing the graft medial to the medial sutures used for the primary tendon repair. The graft will then be tensioned and secured in the anterior-posterior direction using at least two sutures on each side, passed through intact rotator cuff tissue. The suture limbs retained from the laterally placed suture bridge repair anchors will be placed as mattress sutures into the graft, and the graft will be tensioned to a position distal to the repair footprint.

Data for RCR will be recorded:

- Number of anchors
- Quality of repair
- Footprint coverage

3. Assessments

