Eligible patients will be evaluated according to the pre-, intra- and post- operative assessment plans, delineated below, as well as the time and events schedule. All clinical results will be assessed during the period of hospital stay.

A. Preoperative Assessments

The following assessments/tests will be taken prior to patient operative treatment.

- Eligibility criteria, including informed consent.
- Age, gender, height, weight, BMI
- Primary diagnosis
- Medical History
- Physical Exam
- Current medications
- American Society of Anesthesiologists (ASA) risk
- Smoking status
- Imaging of shoulder
- Shoulder outcome surveys (SSV, ASES, Constant, VR12, WORC)

B. Operative Assessments

The following medical information will be collected from the Operative and Anesthesia records.

- Tear size, retraction, quality of tissue
- Length of surgery
- Possible intraoperative arthroscopic photographs

- Implants used
- Quality of repair

C. Postoperative Assessments

The following information will be collected after surgery: standard clinical follow-up PE and history, medications and serial US exams at 6 weeks, 3 months, 6 months, 9 months and 1 year postop, and MRI exam at 1 year postop. All US examinations will be performed by one Board Certified and Fellowship trained Sports Medicine physician in the office and coordinated with scheduled follow-up appointments. Shoulder outcome forms will also be collected at each follow up visit (listed below):

4. Data Collection and Analysis

The primary clinical outcomes to be measured and subsequently evaluated will be the following:

- d. Success as defined by tendon healing after rotator cuff repair, as indicated based on MRI at 1 year.
- e. Comparison of tendon healing will be assessed using US imaging modalities versus MRI at 1 year time point.
- f. Progress of tendon healing based on US will be used as predictive data for 1 year success (based on primary outcome).

The secondary clinical outcomes to be measured and subsequently evaluated will be the patient satisfaction, quality of life, and shoulder function, to be determined with the following outcome measures:

- g. The Veterans Rand 12-item Health Survey (VR-12).
- h. The American Shoulder and Elbow Surgeons Shoulder (ASES)
- i. The Western Ontario Rotator Cuff Index (WORC).
- j. Shoulder activity level as per Brophy et al. [15].
- k. Subjective Shoulder Value (SSV)
- l. Constant Shoulder Score (Constant)

5. Sample Size Justification and Statistical Analysis

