Approximately 70 subjects are needed to assess the primary outcome, measured as the percentage of repairs that heal and remain intact after 1 year. A re-tear rate of 40% is expected in patients who have undergone rotator cuff repair for large and massive rotator cuff tears, based on the current literature (reference ted below). We anticipate that in this study, the percentage of re-tears in the augmented group will be reduced by

approximately half (~20%), while the control group would experience rates of re-tear comparable to what is reported in the current literature (~40%). Reducing this rate by half would be clinically meaningful. An SD of 15% within groups was allowed. Power analysis indicated that 20 patients in each group would provide sufficient power to identify statistical significance in healing rates between the control and augmented groups. With the assumption that the control group will have a failure rate of approximately 40% and the augmented group will have a failure rate of approximately 20%, at least 34 should be randomized in the control group and 26 in the augmented group. It is estimated that an overall fewer percentage of subjects initially randomized to the control group will complete the trial as augmentation may be required due to tear severity and other procedure variables. Those patients randomized to the control arm and withdrawn for repair by augmentation may be followed for safety.

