A power analysis was also considered for shoulder function, a secondary clinical outcome. It demonstrated that at least thirty-four cases must complete the study (seventeen cases in each arm- augmented and control) in order to assess the difference between each group. This sample size was statistically derived by an ASES score power analysis, using a power of 0.8, an effect size d of 0.9, an alpha error probability of 0.05, and an allocation ratio of 1. This is assuming an ASES score of 84 at 12 months postsurgical repair in the augmented group (standard deviation of 16) and 72 (standard deviation of 12) for the control group. The ASES data used was derived from a recently completed ArthroFlex rotator cuff repair study for which data is on file at LifeNet Health. Again, with the assumption that the control group will have a failure rate of approximately 40% and the augmented group will have a failure rate of approximately 20%, at least 30 should be randomized in the control group and 22 in the augmented group to assess a difference in shoulder function.

Once data is acquired for 15 subjects in each group, a post-hoc power analysis will be conducted to confirm that alpha and beta error probabilities are still under the accepted limits.

The primary analysis will be conducted on both the intent to treat and the per protocol populations. The intent to treat population will be comprised of all subjects that have completed rotator cuff repair surgery. The per protocol population will be comprised of all subjects that have completed all study visits and did not have any major protocol violations (e.g., missed visits, noncompliance with postsurgical instructions, etc.). Standard adjustments to analyses for pre-specified or baseline-suggested clinical covariates will be made; these covariate-adjusted analyses will be considered secondary analyses. Primary analysis results will be declared statistically significant if the two-sided p-value is less than 0.05.

Safety analyses will be performed on the intent to treat population and will include the incidence of treatment-emergent AEs and clinically significant changes in vital signs and

physical examinations. Impact of treatment on infection rate, treatment emergent AEs, and changes in vital signs and physical examination will all be assessed.

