Safety data will be summarized with descriptive statistics by treatment group and also by visit, where applicable. AE data will be listed individually and summarized by system organ class and preferred terms within a system organ class for each treatment group.

All statistical comparisons will be made using the Statistical Package for Social Science (SPSS) version 16.0 software. Results will be reported as an aggregate.

Statistical analysis will be performed by the orthopaedic research fellows in conjunction with Cleveland Clinic-Main biostatistician.

6. Study Product Description

ArthroFlex (A-FLEX) is not considered investigational and is currently available. The material is classified as a human and cellular tissue product under Food and Drug Administration (FDA) regulations and thus is not subject to any clinical evaluations before use. LifeNet Health uses several steps to ensure that allograft tissue is safe for use with patients. Extensive donor screening is performed to prevent risk of disease transmissions. There is a medical and social history taken from every donor, and questionable donors are refused. Blood is drawn from each donor for testing to rule out diseases such as HIV, hepatitis, and syphilis. Each section of recovered tissue is tested for any bacteria. In addition, tissue used to make A-FLEX is treated with antibiotic to inactivate bacteria. The tissue is also cleaned thoroughly with detergent, enzymes, and solvent to remove cells from tissue. This MATRACELL™ technology also effectively removes donor DNA from the ADM ensuring a biocompatible scaffold to facilitate repair. All these screenings, tests, and treatments are designed to eliminate the risk of disease transmission. The remaining intact acellular framework contains native growth factors, proteoglycans, hyaluronic acid, collagen, fibronectin, and elastin, therefore promoting wound healing.

A-FLEX is terminally sterilized with low dose gamma irradiation to provide a medical-device grade Sterility Assurance Level (SAL) of 10^{-6} .

Labeling

Since this will be an open-label study, study product will be identified. The Instructions for Use for A-FLEX will be provided in the site study binders.

Storage and Handling of Investigational Product

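### Safety tables rest on completed repairs, apparently grouped by assigned arm, so grafted controls are misgrouped or missing; vital signs are to be analysed but never scheduled

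*Combined protocol and SAP*

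**What the plan says.** **Population.** Section 5 (Sample Size Justification and Statistical Analysis) says: "Safety analyses will be performed on the intent to treat population and will include the incidence of treatment-emergent AEs". It defines that population as follows: "The intent to treat population will be comprised of all subjects that have completed rotator cuff repair surgery". It defines no separate safety or as-treated set.

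**Grouping.** Section 5 also says: "Safety data will be summarized with descriptive statistics by treatment group and also by visit, where applicable". Section 2.D describes both arms by assignment. For the graft arm it says: "Patients randomly assigned into the treatment group will undergo open or arthroscopic rotator cuff repair with A-FLEX graft to augment the repair". For the control arm it says that no graft is used.

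**Crossover.** Section 5 nevertheless expects that a "fewer percentage of subjects initially randomized to the control group will complete the trial as augmentation may be required due to tear severity" and other procedural reasons. It adds: "Those patients randomized to the control arm and withdrawn for repair by augmentation may be followed for safety".

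**Repairs that prove impossible.** Section 2.D, item 3, keeps patients in the study when operative findings rule out a repair, and analyses them as a separate group.

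**Vital signs and physical examination.** The safety analyses are also to cover "clinically significant changes in vital signs and" physical examinations. Section 3.C lists "standard clinical follow-up PE and history" among the postoperative data. The Schedule of Activities marks physical examination at screening only.

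**The concern.** The safety question is what the graft adds to the risk of a repair, so the exposure that matters is whether a graft was implanted. The plan foresees patients for whom exposure and assignment differ, but does not say in which column they are counted and does not require that they be followed. In a trial of 35 per arm, moving or losing one or two events can change a table of uncommon adverse events. Section 8 uses no independent monitoring committee, so these tables are the main comparative safety evidence.

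The completed-repair condition is a second difficulty. A safety set normally begins when the patient is first exposed to study surgery. Here it begins only once a repair has been completed, so an operation that is stopped leaves the set. The one potential serious event that Section 8 links to the graft is an anaphylactoid or anaphylactic reaction, which could be a reason for stopping.

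Third, one of the listed safety analyses appears to have no scheduled data behind it.

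**Working it through.** The plan states no figure on this point, so there is none to reproduce. The check sets the statements side by side and then sizes the effect under stated assumptions.

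**1. Where does an augmented control go?**
- Section 2.D: controls receive no graft. Section 5: some controls may need one. The two statements conflict.
- An augmented control has had a repair completed, so the Section 5 definition keeps that patient in the analysis set. Under an intent-to-treat label, with arms described by assignment, the natural column is control.
- Section 5 also calls the same patient withdrawn, with optional safety follow-up. If follow-up is not done, later events are not captured.
- The plan does not say which of the two applies.

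**2. Who is left out?** A patient whose surgery was started but not completed is outside the set. Section 2.D, item 3, covers those whose repair is ruled out by operative findings, but separately. Whether it covers an operation stopped for another reason, such as a reaction, is not stated.

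**3. Is there a crossover rate in the plan?** No. The nearest figures are the randomisation targets of 34 and 26:
- 20 / (1 − 0.40) = 33.3, rounded up to 34 (stated: 34).
- 20 / (1 − 0.20) = 25 (stated: 26).

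The 40% and 20% are the assumed failure rates, equal to the assumed re-tear rates. They are not crossover rates.

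**4. Size, under assumption.** Inputs: 35 per arm (Section 1). Assumed: all patients complete a repair, everyone in the graft arm receives the graft, *c* controls also receive it, and event risk depends only on graft receipt (*g* with graft, *b* without).

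- Share of graft exposures that are augmented controls: *c* / (35 + *c*).
- Control-column rate if they stay as control: [(35 − *c*)*b* + *c g*] / 35.
- As-assigned difference: *g* minus that rate = (*g* − *b*)(1 − *c*/35).

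| *c* (assumed) | Share of exposures | Share of true difference kept | As-treated split |
|---|---|---|---|
| 3 | 3/38 = 7.9% | 1 − 3/35 = 91.4% | 38 v 32 |
| 7 | 7/42 = 16.7% | 1 − 7/35 = 80.0% | 42 v 28 |

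Example with invented rates *g* = 10% and *b* = 3% (true difference 7 points):
- *c* = 3: control column (32 × 0.03 + 3 × 0.10)/35 = 3.6%; difference 6.4 points.
- *c* = 7: control column (28 × 0.03 + 7 × 0.10)/35 = 4.4%; difference 5.6 points.

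If the augmented controls are omitted instead, the same rates give 10% against 3%, with no dilution. The cost is then the lost exposures (35 observed instead of 38 to 42) and a possible bias of unknown direction.

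**5. Vital signs.** Section 5 names them twice as a safety analysis. They appear in none of the lists in Sections 3.A, 3.B and 3.C and in no row of the Schedule of Activities. Physical examination differs: it is collected in Sections 3.A and 3.C, and only the Schedule disagrees about follow-up.

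**The case against.** - **The grouping rule is not written down.** Section 5 does not expressly say that safety is tabulated by assigned arm, and an as-treated reading is not ruled out. This stands. It sits badly with the intent-to-treat label and the arm descriptions, but the as-assigned reading remains an inference.
- **Events are not simply lost.** A reader might infer that graft-related events disappear. The documents do not support that. Section 8 records all adverse events with their relationship to the device, Section 5 lists them individually, Section 3.B records the implants, and a serious event halts the study and goes to the IRB. What remains is the group incidence tables and the follow-up of withdrawn crossovers.
- **Patients without a repair are not dropped from the study.** Section 2.D, item 3, keeps those whose repair is ruled out by operative findings. This stands, but they are still outside the safety set.
- **Infection as a graft effect.** Section 8 says that infection is a complication of the repair and not of the graft, so it should not be presumed graft-related. Section 5 still plans to assess the impact of treatment on infection rate, and that comparison needs correct grouping.
- **As-treated grouping has its own bias.** Section 5 expects augmentation partly because of tear severity, so grouping by graft received may move harder cases into the graft column. This stands, and is the reason to keep as-assigned tables in support.

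**Conclusion.** The point holds in limited form. As written, the plan would probably misgroup augmented controls or, if they are not followed, omit them. It also leaves patients whose surgery was not completed outside the safety set and lists a vital-sign analysis without a scheduled source. The statements in Sections 2.D and 5 on grafts in controls must be reconciled.

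The size is illustrative only. With an assumed 3 to 7 augmented controls of 35, 8% to 17% of graft exposures are affected. If those patients stay in the control column, 91% to 80% of the true risk difference is kept.

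Two stronger readings are not supported. A reader might derive 7 crossovers from the plan as 35 × (0.40 − 0.20), but those are failure rates and the plan gives no crossover rate. A reader might also conclude that graft risk is understated in every case. Dilution follows only if crossovers are counted as control; if they are omitted, the direction of any bias is unknown.

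This should be corrected. It concerns the safety tables and does not alter the primary healing comparison.

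**What to change.** 1. Define the safety set in Section 5 as all patients in whom study surgery was started, including those whose repair was not completed.
2. Make the main safety tables by whether a graft was implanted, using the implant record in Section 3.B, and give as-assigned tables in support. State that the as-treated split is not randomised and may place more severe tears in the graft group.
3. Make safety follow-up of augmented controls definite, with the same adverse-event collection as for other patients.
4. Reconcile Section 2.D (no graft in controls) with Section 5 (augmentation of some controls expected).
5. Give vital signs a scheduled source, or delete that analysis. Reconcile the physical-examination row of the Schedule of Activities with Section 3.C.

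The cost is SAP and schedule wording, one more set of safety tables, and continued safety follow-up of whichever controls are augmented. Grouping by graft received needs no new data item. Vital signs would need new collection only if that analysis is kept.

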notified. The situation will be discussed among surgical faculty, and if there is a prudent solution, it will be presented to the IRB for approval. If there are no effective solutions, the investigators will have no choice but to discontinue the study.

Data will be reviewed by the PI and physicians conducting the study. The ECM scaffold grafts have not been linked to potentially serious or life-threatening complications. Our research will limit the potential for complications even further by screening and excluding patients with a known allergy to materials of porcine origin. Lastly, the ECM grafts are FDA-approved scaffold material that is indicated for reinforcement or augmentation of soft tissue repairs. In view of this, we will not be deviating from the standard of care by using the ECM allograft and the investigators do not anticipate having to discontinue the study or having to alter the protocol based on interim results. For these reasons, an independent data monitoring committee will not be needed or used.

9. Consent

In a private, outpatient setting, the PI or one of the research coordinators involved in the study will describe in detail the characteristics of the research study. Understandable language will be used. The process of pre-operative assessment, randomization, treatment, data collection and analysis along with the potential risks/benefits of the study are to be described in detail. Furthermore, the methods of maintaining data security and confidentiality will be outlined. The patient is to be explicitly told that he or she does not have to participate in the study and that regardless of his/her decision, will receive the best care this hospital can provide.

The informed consent process will take place during the patient's pre-operative clinical visit. The original consent form will be kept with study records by the principal investigator in a secure location, and a copy of the consent will be given to the subject. The subject's decision to participate will be documented in his or hers electronic record. A copy of the consent may be placed in the hospital record.

10. Principal Investigators

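### In this open-label trial nothing masks the MRI or ultrasound readers to arm or keeps their readings independent, so all three primary outcomes are open to reader bias

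*Combined protocol and SAP*

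**What the plan says.** - **Blinding.** Section 6, Labeling: "Since this will be an open-label study, study product will be identified".
- **Primary outcomes.** The Synopsis (Endpoints, a to c) and Section 4 (the same items, lettered d to f) list three. Outcome a is "Success as defined by tendon healing after rotator cuff repair, as indicated based on MRI at 1 year". Outcome b is "Comparison of tendon healing will be assessed using US imaging modalities versus MRI at 1 year time point". Outcome c uses the course of healing on ultrasound to predict success at 1 year.
- **Ultrasound reader.** Section 3.C: "All US examinations will be performed by one Board Certified and Fellowship trained Sports Medicine physician in the office", timed to coincide with follow-up appointments.
- **MRI reader.** None is identified, and no criterion separates a healed from a re-torn tendon. Section 5 speaks only of repairs that heal and stay intact.
- **Timing.** Section 3.C and the Schedule of Activities: "serial US exams at 6 weeks, 3 months, 6 months, 9 months and 1 year postop, and MRI exam at 1 year postop".
- **Oversight.** Section 8: "Data will be reviewed by the PI and physicians conducting the study". The same section says that there will be no independent data monitoring committee.

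No section mentions masked, central, duplicate or adjudicated image reading.

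**The concern.** Whether a repaired tendon is intact on an image is partly a matter of judgement, most of all in borderline cases. The protocol also carries a stated expectation: Section 5 anticipates that the graft will roughly halve re-tears. A reader who knows the arm and shares that expectation can resolve borderline images in one direction, which creates or enlarges a difference in outcome a.

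A separate problem affects outcomes b and c. Agreement between two imaging methods, or prediction of one by the other, means what it appears to mean only if each is read without knowledge of the other. If not, agreement and apparent predictive value are inflated. This second problem remains even if the graft shows on the images and gives away the arm.

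**Working it through.** **Step 1. What each reader could know, outcome by outcome.** The four ultrasounds at 6 weeks, 3, 6 and 9 months come before the only scheduled postoperative MRI. That fixes which routes of influence are possible.

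| Outcome | Route left open | Route ruled out by timing |
|---|---|---|
| a. Healing on 1-year MRI | MRI reader knows the arm | none |
| b. Ultrasound versus MRI at 1 year | Either 1-year reading is made with the other known; the order of the two is not stated | none |
| c. Serial ultrasound predicts 1-year success | MRI reader knows the earlier ultrasounds | 1-year MRI influencing the 6-week to 9-month scans |

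**Step 2. Illustration for outcome a.** The plan has no figure to reproduce here, since it gives no misreading rate.

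Inputs from the plan: 35 per arm (Section 1); two-sided 0.05 (Section 5). Assumed: true re-tear 30% in both arms, all 35 per arm evaluable, and readings shifted by 2.5 or 5 points in opposite directions. The plan names no test for healing, so two are shown.

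Pooled z: z = (x/35 − y/35) / √[p(1 − p)(2/35)], with p = (x + y)/70, rejecting if |z| > 1.96. The rejection probability is the sum, over all pairs (x, y) that reject, of Bin(x; 35, control rate) × Bin(y; 35, graft rate). The same sum is taken over the pairs for which Fisher's exact p is below 0.05.

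| Rates as read (control, graft) | Pooled z | Fisher's exact |
|---|---|---|
| 30%, 30% | 5.1% | 2.8% |
| 32.5%, 27.5% | 7.5% | 4.4% |
| 35%, 25% | 15.0% | 9.9% |

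With the z test, 6.7 of the 7.5 points and 14.8 of the 15.0 points favour the graft. The shifts are small in patients: 0.025 × 35 = 0.9 per arm and 0.05 × 35 = 1.75 per arm. Whatever the test, they add a spurious difference of 5 or 10 points. The planned difference is 40 − 20 = 20 points, so that is a quarter or a half of it.

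*Sensitivity.* Section 5 states: "A re-tear rate of 40% is expected in patients who have undergone rotator cuff repair for large and massive rotator cuff tears". With 40% in both arms and misreading in the graft arm only, calling 10% of its re-tears intact gives 0.40 × 0.9 = 36%, and calling 20% intact gives 0.40 × 0.8 = 32%. The z-test false-positive rate goes from 4.8% to 6.4% or 10.9%. With 20 evaluable per arm and the 30% base rate, the z-test figures for the two shifts are 6.7% and 11.0%.

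**Step 3. Illustration for outcome b.** Assumed: 30% failures on MRI, ultrasound sensitivity and specificity of 80%, and a fraction c of discordant 1-year ultrasound readings changed to match a known MRI.

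- Observed agreement: Po = 0.8 + 0.2c.
- Ultrasound failure rate: u = 0.3(0.8 + 0.2c) + 0.7 × 0.2(1 − c).
- Chance agreement: Pe = 0.3u + 0.7(1 − u).
- Kappa = (Po − Pe)/(1 − Pe).

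Results:
- c = 0: u = 0.38, Pe = 0.548, kappa = 0.252/0.452 = 0.56.
- c = 0.25: u = 0.36, Pe = 0.556, kappa = 0.294/0.444 = 0.66.
- c = 0.5: u = 0.34, Pe = 0.564, kappa = 0.336/0.436 = 0.77.

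**The case against.** The Labeling sentence concerns product identification, not image reading, and an open-label surgical trial can still have masked readers. That is right: the documents show a missing safeguard, not a bias that has occurred.

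Three stronger readings are tempting, and the documents do not support them:

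- *That readers will be told the arm, or that the operating surgeon reads the images.* Neither is stated. Section 3.C gives ultrasound to a sports medicine physician and Section 2.D gives surgery to orthopedic surgeons, which is some separation. Section 7 also restricts access to the REDCap database. That protection is weak, because the Synopsis names EPIC as a data source too and nothing keeps a reader out of the chart.
- *That knowledge of the MRI could taint the whole ultrasound series.* The first four scans come before it, so only the 1-year pair can be affected in both directions.
- *That the trial's false-positive rate is 7.5% or 15%.* Those figures depend on chosen shifts, a 30% base rate that is not a planning input, full follow-up in a trial whose log of changes cites large drop-out, and a test the plan does not name. With Fisher's exact test the smaller shift stays below 5%.

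Masking to arm will also be imperfect. The graft may be visible, and an unmasked patient scanned face to face may disclose it. This limits the remedy for outcome a, but does not prevent keeping the MRI and ultrasound readings independent of each other.

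**Conclusion.** The point holds as a gap in the plan. An open-label trial rests its main endpoint on an image judgement, with no reader identified for the MRI, no reading criterion and no masking, and it makes US-MRI comparisons primary without requiring independent readings. The exposure differs by outcome: knowledge of the arm for a, either direction at 1 year for b, and an MRI reader's knowledge of earlier ultrasounds for c.

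The size is unknown. The calculations show only that, at 35 per arm, one or two borderline readings per arm can matter: under the stated assumptions, false positives reach 7.5% to 15.0% (pooled z) or 4.4% to 9.9% (Fisher's exact). The omission rests on the text alone; the numbers rest on assumption. It should be corrected because doing so is cheap and protects all three primary outcomes.

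**What to change.** Add to Sections 3.C and 4:

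1. **MRI.** State by role who makes the endpoint reading. It is made without the arm, the operative note or any ultrasound result from 6 weeks to 1 year. Hiding only the 1-year ultrasound would leave open the route that affects outcome c. The reading goes on an intact / not-intact form fixed in advance and separate from the routine clinical report, so that routine reporting is unaffected.
2. **Ultrasound.** The physician records each scan before opening the operative note. Patients are asked not to disclose their arm. The 1-year scan is recorded before the MRI report is seen.
3. **Locking.** Both 1-year forms are locked before results are shared.
4. **Check on masking.** Each reader records a guess of the arm, and the guesses are reported by arm.

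The cost is protocol wording, two short forms and one extra research reading per MRI. It needs no new visits or scans and can use existing readers, provided that whoever now reads the MRI can be kept from the arm; the documents do not say who that is. The downside is that masking to arm will be partial, because the graft may be visible and patients may disclose it.
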